7.3.5 CFB by Visit in Permitted Rescue Medication Use

Permitted rescue medication will be provided to subjects from Visit 2 for rescue use if needed for endometriosis associated pain throughout the study. Use of analgesic medication will be reported by subjects in the e-Diary on a daily basis from Visit 2 through the Follow-up period.

The average pill count of permitted rescue medications along with CFB will be summarized by visit measurement including Baseline, Week 6, Week 12 and Week 24 (following the definitions in sections of 7.2.1 and 7.3.1 for the time window). The percentage of days with analgesic rescue use which will be calculated based on those days in the visit window with non-missing data will be summarized by visit.

In addition, the pill count of rescue medications at Week 12 separated by Tier 1 and Tier 2 (following the definitions in sections of 7.2.1 for the time window) as the dependent variable, treatment comparison may be compared using an ANCOVA model with treatment and region as the main effects and baseline of pill count as a continuous covariate.

The correlation between the use of rescue medications (in terms of pill count) and DYS and NMPP measured by NRS at Week 12 measurement will be explored by summary statistics including Pearson and Spearman correlation coefficients and graphical presentation (e.g., scatter plot).

Daily use of permitted rescue medications will be listed.

7.3.6 Change in Menstrual Period Heaviness from Baseline by Visit

Descriptive statistics will be presented for the changes of days of menstrual period and menstrual cycle, and the changes of mean scores of heaviness (bleeding) collected from eCOA at Week 6, Week12 and Week 24 measurements.

Scores of heaviness (bleeding) for each subject will be listed.

8. SAFETY

All safety summaries and analyses will be based upon SAF and is as same as PAS to focus on the same population as primary efficacy data analysis. All safety analyses will be based on observed data. Unless otherwise specified, missing data will not be imputed.

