9.3 Populations for Analyses

For purposes of analysis, the following analysis sets will be used:

Table 9-1 Populations for Analyses

Population (Analysis Set)	Description
Enrolled Analysis Set	All subjects who signed the ICF (including screening failures).
Full Analysis Set (FAS)	This analysis set includes all randomized subjects who take at least one dose of IMP. For the FAS, subjects are assigned to a treatment group based on the randomization schedule, regardless of the treatment actually received. FAS will be used for all efficacy analyses.
Per Protocol Analysis Set (PPS)	The PPS comprises a subset of the FAS who do not have protocol deviations that could significantly affect the results for the primary endpoints. Subjects' inclusion/exclusion from the PP population will be determined and documented prior to the database lock and unblinding. PPS will be used for the primary and secondary efficacy endpoints.
Safety Analysis Set	The Safety Analysis Set consists of all subjects who received at least one dose of IMP. Subjects will be analyzed according to the IMP they actually received. Safety Analysis Set will be used for all safety analyses.
PK Analysis Set	The PK analysis set consists of all subjects in the Safety Analysis Set with at least one drug concentration value and have no major protocol deviation that could significantly impact PK assessment.

Version 6.0 61 of 138 April 11, 2024

Immunogenicity analysis	The immunogenicity analysis set consists of all subjects in the
set	Safety Analysis Set with at least one immunogenicity value.

All protocol deviations will be reviewed and classified regarding how they affect clinical and analysis outcomes during the Blinded Data Review Meetings. Subjects may be excluded from the PPS and PK Analyses Set.

The FAS will be the primary analysis set for all efficacy analyses and the PPS will be used to demonstrate robustness of results for the primary and secondary efficacy endpoints.

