1. INTRODUCTION

HMI-115 is a highly specific human monoclonal antibody that will be investigated for safety and efficacy in pre-menopausal women with moderate to severe endometriosis associated pain.

A First in-human (FiH) study with HMI-115 has already established the safety and tolerability of HMI-115 when administered subcutaneously in post-menopausal women aged between 45 to 65 years in single doses up to 240 mg and multiple doses up to 90 mg once every 2 weeks (Q2W) for 6 weeks. This study aims to evaluate the safety and efficacy of HMI-115 versus a placebo in pre-menopausal women aged 18 to 49 years diagnosed with moderate to severe endometriosis associated pain.

The analyses described in this Statistical Analysis Plan (SAP) are based upon the following study documents:

- Study Protocol Version 6.1 (19 Sep 2024)
- Electronic Case Report Form (eCRF), Version 6.0 (12 Dec 2023)

Data will be summarized and listed according to the SAP. The details will be reflected in the document of Table, Listing, and Figure Shells.

The planned analyses identified in this SAP may be included in clinical study reports (CSRs), regulatory submissions, or future manuscripts. Also, post hoc exploratory analyses not necessarily identified in this SAP may be performed to further examine study data. Any post hoc, or unplanned, exploratory analyses performed will be clearly identified as such in the final CSR.

In addition, the SAP V1.3_special version for research paper publication is generated for the requirement of research paper publication only. Compared to the SAP V1.3, the change is that the SAF will be same as the PAS for all safety analysis.

PROJECT OVERVIEW

[figure not shown]

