3.3 Analysis Sets

For purposes of analysis, the following analysis sets will be used:

Analysis Set	Description
Enrolled Analysis Set (ES)	All subjects who signed the ICF (including screening failures).
Full Analysis Set (FAS)	All randomized subjects who take at least one dose of IMP. For the FAS, subjects are assigned to a treatment group based on the randomization schedule, regardless of the treatment actually received.
Primary Analysis Set (PAS)	All subjects in the FAS who have surgical diagnosis. PAS will be the primary analysis set for all efficacy analyses.
Per Protocol Analysis Set (PPS)	A subset of the PAS who do not have protocol deviations that could significantly affect the results for the primary endpoints. Subjects' inclusion/exclusion from the PPS will be determined and documented prior to the database lock and unblinding. PPS will be used to demonstrate robustness of results for the primary and secondary efficacy endpoints.
Safety Analysis Set (SAF)	All subjects who received at least one dose of IMP. Subjects will be analyzed according to the IMP they actually received. SAF

	will be used for all safety analyses. In the SAP V1.3 special version for research paper publication, the SAF will be same as the PAS.
PK Analysis Set (PKS)	All subjects in the SAF who received active treatment with at least one drug concentration value, and have no major protocol deviation that could significantly impact PK assessment.
Immunogenicity Analysis Set	The immunogenicity analysis set consists of all subjects in the SAF with at least one immunogenicity value.

All protocol deviations will be reviewed and classified regarding how they affect clinical and analysis outcomes during the BDRM. Subjects may be excluded from the PPS and PKS.

Summary of the number and percentage of subjects in each analysis set with exception of the ES by treatment group and overall, based on all randomized subjects with reasons for exclusion from each analysis set will be provided.

A by-subject listing of analysis set details will be provided on the ES. This listing will be presented by treatment group and will include center, subject identifier, inclusion/exclusion flag for each set and reason for exclusion from each set.

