7.2.4 Supplementary Analyses

The primary efficacy analysis described in section 7.2.2 will be repeated on the PPS and FAS.

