7.2.5 Other Analyses

Percentage Change from Baseline

The percentage change of DYS measured by NRS from Baseline to Week 12 will be performed the same method as analysis of primary outcome in section 7.2.2.

Percentage change from Baseline = (the mean of Visit - the mean of Baseline) / the mean of Baseline)*100%.

The Visit refers to Week 12 measurement or other post-baseline visits.

E-diary Compliance

All subjects will be administered an e-Diary after adequate training at Visit 2. Subjects are required to record uterine bleeding and endometriosis-associated pain every day for the entire duration of the study (until end of study). The use of rescue medications for endometriosis-associated pain will also be recorded. Compliance to e-Diary filling will be summarized for treatment group using PAS including the following variables:

Planned e-Diary Duration (days) = Date of Last Study Visit – Date of Visit 2 +1.

If a subject completed or discontinued the study early, the date of last study visit will be the day of EOS. If a subject is still ongoing, the date of last visit will be replaced by the date of last e-Diary record or last visit date (if applicable), whichever comes last.

- Total days with e-Diary (days) is the total days during study with e-Diary data. All days with non-missing e-Diary regardless of correction or refilling will be included.
- Compliance to e-Diary (%) = (Total Days with e-Diary / Planned e-Diary Duration) × 100.

Based on above calculation formula of e-Diary compliance, another compliance (%) will be calculated to exclude those days with missing and corrected/refilled e-Diary from today days with e-Diary (days).

E-diary data will be listed on the PAS.

Receiver Operating Curve (ROC) Analysis for Determination of Thresholds for Reduction in Pain

The ROC analysis will contain all subjects who received at least one dose of IMP.

- Subjects who a) prematurely discontinue before Week 13, or b) either prematurely discontinue at or after Week 13 but are missing Week 13 PGIC will be assigned a PGIC response of "No change" (PGIC Non-responder).
- Observed values of DYS measured by NRS without any imputation will be used for ROC analysis.

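### The publication version of the SAP limits all safety tables to surgically diagnosed subjects, so harms in other dosed subjects drop out of the paper

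*SAP*

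**What the plan says.** - Protocol V6.0, Section 9.3: "The Safety Analysis Set consists of all subjects who received at least one dose of IMP". Subjects are analysed by the IMP they actually received, and the set serves all safety analyses.
- SAP Section 3.3, SAF row, opens the same way: "All subjects who received at least one dose of IMP. Subjects will be analyzed according to the IMP they actually received". The row then adds that in the special version for the research paper "the SAF will be same as the PAS". The PAS is the part of the FAS with a surgical diagnosis.
- SAP Section 1 says this version exists solely for the paper: "Compared to the SAP V1.3, the change is that the SAF will be same as the PAS for all safety analysis".
- SAP Section 8 applies the rule to all safety summaries and gives the reason: they "analyses will be based upon SAF and is as same as PAS to focus on the same population as primary efficacy data analysis".
- SAP Section 10 explains why surgically diagnosed subjects became the primary analysis population and says the non-surgical population will serve as a supplementary analysis. Its numbered list of changes from the protocol does not include the SAF change.

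**The concern.** Diagnosis method may reasonably define the population for an efficacy question. It does not bear on whether a dosed woman's adverse event should be counted. The only reason Section 8 offers is a common denominator with the efficacy tables. If the paper follows this version, an AE, SAE, death, QTcF value or bone density result in a dosed subject without a surgical diagnosis is absent from its safety tables.

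The same subject can still count elsewhere. SAP Section 7.2.4 states: "The primary efficacy analysis described in section 7.2.2 will be repeated on the PPS and FAS". For the pain-reduction threshold, Section 7.2.5 states: "The ROC analysis will contain all subjects who received at least one dose of IMP". Her data could help set the threshold for a meaningful improvement while her SAE goes unreported in the paper's tables.

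**Working it through.** **1. Who is removed.** The PAS is the FAS minus subjects without a surgical diagnosis, and the FAS is everyone randomised and dosed. With the SAF set equal to the PAS, the subjects removed are the dosed subjects without a surgical diagnosis.

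**2. Are there any?** Protocol V6.0 inclusion criterion 2 names laparoscopy or laparotomy, which taken alone could make the two sets coincide. SAP Section 10 indicates otherwise: it assigns a role to the non-surgical population and drops a former surgical versus non-surgical subgroup. Section 4.1 also tabulates diagnosis method and reports demographics on the FAS and PAS separately. The SAP rests on Protocol V6.1, which was not supplied, so the number is unknown.

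**3. Which outputs are cut.** Sections 8.1 to 8.4 fall under the Section 8 rule: AEs, AESIs, deaths, SAEs, discontinuations due to AEs, laboratory tests, vital signs, ECG, ultrasound and DXA. Section 5 exposure names the SAF. The PK and immunogenicity sets in Section 3.3 are built from the SAF and shrink with it.

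**4. Does another table fill the gap?** The FAS and PPS supplements in Sections 7.1, 7.2.4 and 10 are for efficacy. The sentence in Section 10 on the non-surgical population leads to no safety output. Disposition (Section 3.1) would still show withdrawals and IMP discontinuations with reasons, but not the AE and SAE tables.

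**5. A conflict inside the SAF row.** The opening definition assigns subjects by IMP received. The PAS inherits assignment by randomisation from the FAS. The row therefore contradicts itself on treatment assignment as well as on membership.

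**6. Illustrative size.** The plan gives no figure to reproduce on this point. Planned numbers are 4 × 38 = 152 subjects, of whom 3 × 38 = 114 receive HMI-115. Assume all are dosed and a share *p* lacks a surgical diagnosis, spread evenly over arms; the values of *p* are assumptions. With *n* retained on HMI-115:
- one-sided 95% upper bound after zero events: 1 − 0.05^(1/n)
- chance of seeing at least one event at a true 2% rate: 1 − 0.98^n

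| p | Excluded of 152 | Lost of 114 | n | Upper bound | Chance of ≥1 event |
|---|---|---|---|---|---|
| 0 | 0 | 0 | 114 | 2.59% | 0.900 |
| 5% | 8 | 6 | 108 | 2.74% | 0.887 |
| 10% | 15 | 11 | 103 | 2.87% | 0.875 |
| 20% | 30 | 23 | 91 | 3.24% | 0.841 |
| 30% | 46 | 34 | 80 | 3.68% | 0.801 |

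The loss of precision is small at the low end and moderate at the high end.

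**The case against.** The restriction is deliberate, stated openly in three places, and confined to one document. Because Section 1 presents it as the change from V1.3, V1.3 by implication keeps the all-dosed set, so the CSR, SAE reporting and DMC review appear untouched. Protocol Section 10.1.6 also commits to posting a summary of main results on a public registry. Section 10 shows that the PAS was not chosen arbitrarily: it cites an FDA request and the global protocol. The AE, death and SAE listings in Sections 8.1 and 8.2 name no analysis set, so they may not be cut. Finally, if the SAF rule is all that separates this version from V1.3, deleting it removes the version's reason to exist.

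Most of this limits the scope of the concern and does not answer it. The request cited in Section 10 concerns the primary analysis; nothing there asks for a safety restriction. The registry commitment names no safety set. Papers seldom print subject listings. Telling SAP readers about the restriction does not oblige the paper to show all-dosed results. The last point does stand in part: full deletion amounts to reporting safety under V1.3, and a sponsor that wants to keep this version can use the side-by-side remedy. It is also right that the number omitted is unknown, and criterion 2 of V6.0 cannot settle it.

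**Conclusion.** The concern holds for the publication version and should be fixed. As written, its safety summaries exclude dosed subjects on a criterion unrelated to exposure, contrary to Protocol V6.0 Section 9.3 and to the SAP's own opening definition. Confidence in this reading is high. The size is not known: the table above rests on assumed shares of 5 to 30%, full dosing of 152 subjects and even spread over arms. The conclusion does not depend on those figures, since an observed serious event left out matters even if very few subjects are excluded. It does not follow that the trial lacks an all-dosed safety analysis; Section 1 implies that V1.3 provides one.

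**What to change.** **Preferred.** In SAP Section 8, delete the words that equate the SAF with the PAS and the reason attached to them. Delete the matching override sentences in Sections 1 and 3.3. The paper's main safety and exposure tables then use all dosed subjects by IMP received, and PAS-restricted safety can appear as a labelled supplement.

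**Minimum.** Keep the version, but require all-dosed AE, SAE, death and IMP-discontinuation tables beside the PAS tables, list the SAF change in Section 10, and state how treatment is assigned in the PAS safety tables.

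In either case, footnote that the main safety and efficacy tables have different denominators. The counts needed are already planned in Section 3.3: "Summary of the number and percentage of subjects in each analysis set with exception of the ES by treatment group and overall", with reasons for exclusion.

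**Cost.** Wording in three sections and a footnote for the preferred route; some added tables and a Section 10 entry for the minimum. The all-dosed tables by implication already exist under V1.3. The small downside is that safety and efficacy denominators differ.

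A separate, lesser point that does not arise from the SAF change: Section 6 summarises concomitant medication, which the protocol lists as a safety endpoint, on the PAS. Once the SAF is restored, that table should use it.

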8.1 Adverse Events

All AEs will be coded using the Medical Dictionary for Regulatory Activities (MedDRA) 24.0 or a later version.

Treatment Emergent Adverse Events (TEAEs) will be tabulated and are defined as those AEs with a start date on or after the first administration of IMP.

Where dates are missing or partially missing, AEs will be assumed to be treatment-emergent, unless there is clear evidence (through comparison of partial dates) to suggest that the AE started prior to the first administration of IMP. For AEs with completely unknown dates, dates will be shown as NK (unknown) in the listings. For AEs with partially start and/or end dates, the available day, month and year components will be shown in listing.

Frequencies and percentages of subjects with TEAEs will be calculated for each treatment group as follows:

- Overview incidence of all AEs
- A summary of the number and percentage of subjects reporting a TEAE by treatment, SOC, and PT
- A summary of the number and percentage of subjects reporting a TEAE by treatment, causality, SOC, and PT
- A summary of the number and percentage of subjects reporting a TEAE by treatment, severity, SOC, and PT
- A summary of the number and percentage of subjects reporting a AESI by treatment, SOC, and PT
- A summary of the number and percentage of subjects reporting a AESI by treatment, causality, SOC, and PT

Adverse event summaries will be ordered in terms of decreasing frequency for SOC, and PT within SOC, in the overall treatment groups, and then alphabetically for SOC, and PT within SOC. The actual version of the MedDRA coding dictionary used will be noted in the AE tables.

For each subject and each adverse event, the worst severity recorded will be attributed and used in the by-severity summaries. Similarly, the worst causality (most related to treatment) will be attributed and used in the by-causality summaries. If severity or causality is missing, a conservative approach for AE assessment (taking into account the worst case) will be followed.

Below listings will be provided:

- A by-subject listing of AEs
- A by-subject listing of AESIs

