8.4.1 Time Period and Frequency for Collecting AE and SAE Information

All AEs and SAEs will be collected from the signing of ICF until the end of study participation at the time points specified in the SoA (Section 1.3).

All SAEs will be recorded and reported to the Sponsor or designee within 24 hours, as indicated in Section 10.3. The Investigator will submit any updated SAE data to the Sponsor within 24 hours of it being available.

Investigators are not obliged to actively seek AEs or SAEs after the end of study participation. However, if the Investigator learns of any SAE, including a death, at any time after a subject has been discharged from the study, and he/she considers the event to be reasonably related to IMP or study participation, the Investigator must promptly notify the Sponsor.

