9.4.8.2 Adverse Events

Adverse events will be coded using the Medical Dictionary for Regulatory Activities (MedDRA) dictionary. Treatment-emergent AEs (TEAE) will be summarized for each treatment group. TEAEs are defined as AEs with a start date on or after the first dose of IMP. Frequencies and percentages of subjects with TEAEs will be calculated for each treatment group as follows:

- Any event
- By system organ class, preferred term and relationship
- By system organ class, preferred term and maximum severity
- Any event and by system organ class and preferred term for events resulting in death
- Any event and by system organ class and preferred term for events resulting in IMP discontinuation
- Any event and by system organ class and preferred term for serious adverse events
- Events of special interest (refer to Section 10.3.1)

A listing by treatment group of TEAEs grouped by body system, and preferred term with subject ID numbers will be generated. Listings of all treatment-emergent SAEs, AEs leading to death, and AEs leading to discontinuation will be generated.

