- The Investigator is obligated to perform or arrange for the conduct of supplemental measurements and/or evaluations as medically indicated or as requested by the Sponsor to elucidate the nature and/or causality of the AE or SAE as fully as possible. This may include additional laboratory tests or investigations, histopathological examinations, or consultation with other health care professionals.
- During the course of the study, new or updated information will be recorded in the
 originally completed eCRF. The Investigator will submit any updated SAE data to the
 Sponsor within 24 hours of receipt of the information.
- Any AEs that are unresolved at last visit in the study are followed up by the Investigator
 for as long as medically indicated but without further recording in eCRF. For any subject
 with ongoing AE(s)/SAE(s) at the end of the study, the Sponsor retains the right to request
 additional information if judged necessary.

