1.1 Study Design

This is a Phase 2, multicenter, double-blind, placebo-controlled, randomized study to assess the safety and efficacy of HMI-115 subcutaneously administered monoclonal antibody versus placebo in pre-menopausal women with moderate to severe endometriosis-associated pain. The planned study regions include China, the United States of America (USA) and European countries.

The study will comprise of three periods:

1. Screening Period of up to 75 days prior to first dose
 - Screening Visit 1
 - Screening Visit 2 (at least 35 days before Visit 3 to ensure at least 5 weeks baseline pain score obtained before randomization)
2. Treatment Period (12 weeks). Subjects will be given subcutaneous (s.c.) injections Q2W (once every 2 weeks).
3. Follow-up Period of 12 weeks.

Figure 1: Study Design of the Study

IMP: investigational medicinal product.

Eligible subjects will be randomized into four arms: placebo, 60 mg, 120 mg, and 240 mg HMI-115 in a 1:1:1:1 ratio with 38 subjects/arm. The randomization will be stratified with two stratification factors 1) region and 2) participation in the intensive Pharmacokinetics(PK) sampling subset.

A subject is considered to have completed the study if she has completed all phases of the study including the last scheduled procedure (follow-up at Week 25 for safety and to cover 5 half-lives) as shown in the Schedule of Activities (SoA) (Section 1.3 of Protocol).

The end of this clinical study is defined as the date of the last visit of the last subject in the study or last scheduled procedure shown in the SoA (Section 1.3 of Protocol) for the last subject in the study globally.

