1.3.2 Safety and Tolerability endpoints(s)

1.3.2.1 Adverse Events (AEs)

All AEs will be collected from the signing of informed consent form (ICF) until the end of study participation at the time points specified in the SoA (Section 1.3 of Protocol).

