8.2 Deaths, Serious Adverse Events, and Other Significant Adverse Events

Below summaries will be provided:

- A summary of the number and percentage of subjects reporting a TEAE resulting in death by treatment, SOC and PT
- A summary of the number and percentage of subjects reporting a TEAE resulting in IMP discontinuation by treatment, SOC and PT

- A summary of the number and percentage of subjects reporting a SAE by treatment, SOC and PT
- A summary of the number and percentage of subjects reporting a SAE resulting in IMP discontinuation by treatment, SOC and PT

Listings to be provided include:

- A by-subject listing of AEs leading to death
- A by-subject listing of TEAEs leading to IMP discontinuation
- A by-subject listing of treatment emergent SAEs

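### TEAEs are defined by start date only, so a screening-onset event that worsens on treatment can drop out of the TEAE summaries; separately, the SAP's SAE summaries carry no treatment-emergent limit

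*SAP*

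**What the plan says.** **Definition.** In SAP 8.1, TEAEs "are defined as those AEs with a start date on or after the first administration of IMP". Protocol 9.4.8.2 agrees: "TEAEs are defined as AEs with a start date on or after the first dose of IMP". The SAP's rule for missing or partial dates also turns on onset alone: the event counts as treatment-emergent unless there is clear evidence "to suggest that the AE started prior to the first administration of IMP".

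**Collection window.** Protocol 8.4.1: "All AEs and SAEs will be collected from the signing of ICF until the end of study participation". SAP 1.3.2.1 says the same. SAP 1.1 allows a "Screening Period of up to 75 days prior to first dose".

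**Recording.** Protocol 10.3.3: "During the course of the study, new or updated information will be recorded in the" eCRF that was first completed for the event. Protocol 10.3.1 counts an exacerbation of a pre-existing condition as an AE. For the by-severity tables, SAP 8.1 attributes to each event the worst severity recorded.

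**Outputs.** The incidence, causality and severity summaries in SAP 8.1, and the death and IMP-discontinuation summaries in SAP 8.2, are of TEAEs. The two SAE summaries in SAP 8.2 are not so limited; the first reads "A summary of the number and percentage of subjects reporting a SAE by treatment, SOC and PT". The SAE listing in the same section covers treatment-emergent SAEs only. Protocol 9.4.8.2 places its SAE table under a lead-in that counts subjects with TEAEs. The AESI summaries in SAP 8.1 do not say TEAE themselves but sit under a TEAE lead-in.

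**The concern.** A definition based only on onset has no place for an event that is already present at first dose and gets worse afterwards. This protocol treats worsening as something to watch: its AE definition covers exacerbated disease, and its AESI descriptions for mood and for headache both name worsening. If such an event keeps its pre-dose start date, it is missing from the tables that compare tolerability by dose, including the table of events that led to stopping IMP.

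The rule also separates like from like. A condition known before consent goes into medical history, so its exacerbation on drug is a new AE with a post-dose onset and is counted. The same symptom starting the day after consent, and worsening on drug in the same way, may not be.

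The SAE outputs have a different fault. A table and a listing meant to describe the same events use different scopes, so they would not reconcile.

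**Working it through.** No alpha, power or variance enters this point, and the plan states no figure to reproduce. The check is to trace cases through the rules as written.

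**1. Who is affected.** Three conditions must all hold: onset between consent and first dose (a window of up to 75 days), still ongoing at Day 1, and worse on or after first dose. Conditions that predate consent are outside the gap.

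**2. Which start date applies.** Neither document says whether an increase in severity opens a new AE record or updates the old one. Two passages lean towards one record with the original date: Protocol 10.3.3 sends updates to the form first completed, and the worst-severity rule in SAP 8.1 makes most sense if one event can carry several severities. One passage leans the other way: Protocol 10.3.1 accepts an exacerbation as an AE, which could have its own onset date.

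**3. Cases, all in a dosed subject.** A treatment-emergent SAE is taken to be an SAE that meets the TEAE definition.

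| Case | TEAE as defined? | TEAE summaries | SAE summaries, SAP 8.2 | Listings |
|---|---|---|---|---|
| A. Condition predates consent; on-drug exacerbation entered as an AE | Yes | In | In, if serious | In |
| B. AE starts in screening; on-drug worsening entered as a separate AE | Yes | In | In, if serious | In |
| C. As B, but worsening kept on the original record | No | Out | In, if it becomes serious | In the AE listing (and the AESI listing if it qualifies); not in the TEAE discontinuation listing or the SAE listing |
| D. SAE that starts in screening | No | Out | In | In the AE listing; not in the SAE listing |

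B and C are the same clinical course. Only the form of entry differs, and it decides whether the event is in the by-dose tables. If C leads to stopping IMP, it is in neither the discontinuation summary nor the discontinuation listing, since both are limited to TEAEs.

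**4. SAE scope.** Case D is in the SAP's SAE table under the subject's arm but absent from the SAP's SAE listing. It would also be absent from the protocol's SAE table. The three outputs cannot all be right.

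**5. Size.** Let p be the proportion of subjects with a screening-onset AE ongoing at Day 1, w the proportion of those who worsen on treatment, and k the proportion of those worsenings kept on the original record. The proportion of subjects affected is p × w × k. The documents give none of the three. What can be said is the scale of a single case: at the planned 38 per arm, one subject moves an arm's incidence by 1/38 = 2.6 percentage points.

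**The case against.** **Loss is conditional.** A reader might infer that every such event is absent from every TEAE table. The documents do not support that. Protocol 10.3.1 lets a site enter the exacerbation as its own AE (case B), and CRF completion guidelines, which could settle the matter, are not among the documents. The worst-severity rule is also compatible with several records of one event. This stands, and the conclusion is limited to case C. It does not remove the point: classification would then depend on how each site enters the event.

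**AESIs.** A reader might infer that headache, acne and mood change are common before treatment in these women, so the loss is large. The documents give no such rates. The exclusion criteria remove chronic headache that needs chronic therapy and would interfere with pain assessment, and Protocol 2.1 says that obvious pre-existing mood disorders will not be recruited. The mood and headache AESI descriptions name worsening, which favours an on-treatment entry. The frequency claim therefore has no support. The AESI wording still sits badly with a TEAE rule that ignores worsening.

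**Nothing vanishes.** The by-subject AE and AESI listings are unrestricted, and the overview of all AEs might include these events although its lead-in refers to TEAEs. That is correct, but a listing does not give rates by dose.

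**SAE tables.** Counting every SAE in dosed subjects is cautious, and since randomization takes place on Day 1, screening SAEs should not systematically favour an arm. The protocol already supplies the limit. So this is a wording and reconciliation fault in the SAP, not a source of bias. The unrestricted table even helps in one respect: an event in case C that becomes serious on drug is still counted there.

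**Conclusion.** The point holds in a limited form. Both documents define a TEAE by onset alone. Followed as written, that rule leaves on-treatment worsening of a screening-onset AE out of the TEAE summaries of incidence, severity, causality and IMP discontinuation whenever the worsening stays on the original record. The text leans towards that practice without fixing it. The group concerned is narrow (onset after consent, ongoing at Day 1, then worse), and its events remain in the AE listing.

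The SAE mismatch is certain from the wording: a dosed subject's screening SAE is in the SAP's SAE table but not in its SAE listing, and the table is wider than the protocol's. SAEs in screen failures do not enter, because the safety set is restricted to dosed subjects.

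The number of subjects affected cannot be derived. Any per-arm count would rest wholly on assumed rates of ongoing screening AEs and of worsening, so none is offered. The change is worth making because the rule decides what appears in the main by-dose safety tables and one clause corrects it.

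**What to change.** 1. In SAP 8.1 and Protocol 9.4.8.2, define a TEAE as an AE that starts on or after the first IMP administration, or that starts earlier and increases in severity or becomes serious on or after it. If the protocol is not amended, record the difference in SAP section 10.
2. State how an increase in severity and its date are recorded, for example as a new AE record linked to the old one. For data already collected, use recorded severity changes where they exist and note the limitation.
3. Extend the missing-date rule in SAP 8.1 to cover the date of worsening.
4. Label the two SAE summaries and the AESI summaries as treatment-emergent, to match the SAE listing and the protocol, and list pre-dose SAEs separately. Make this change together with item 1: limiting the SAE tables without the worsening clause would remove screening-onset events that become serious on drug.

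The cost is a few sentences in the SAP and protocol, a CRF completion instruction and relabelled table shells. A few more events would count as TEAEs. Dates of worsening may not be recoverable for data already collected, so the new definition may be only partly applicable to those records.
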